### **4.6.2. Adverse Events**

Adverse events will be coded using the MedDRA (version 17.0) coding system and displayed in tables and data listings using system organ class (SOC) and preferred term (PT).

Analyses of AEs will be performed for those events that are considered treatment-emergent, where a treatment-emergent adverse event (TEAE) is defined as any AE with onset after Day 1 of drug administration. TEAEs will also be summarized. If the start date of an AE is partially or completely missing, the date will be compared as far as possible with the date of the start of administration of study drug. If the start date/time of an AE is partially or completely missing, the date/time will be compared as far as possible with the date/time of the start of administration of study drug. The AE will be assumed to be treatment emergent if it cannot be definitely shown that the AE did not occur or worsen during the treatment-emergent period (worst case approach). The following approach will be taken:

- If the start time of an AE is missing but the start date is complete, an AE will only be excluded as being treatment emergent if the start date is before the date of Day 1 study drug administration or if the stop date/time is before Day 1 study drug administration.
- If the start time and day are missing but the start month and year are complete, an AE will only be excluded as being treatment emergent if the start month/year is before the month/year of Day 1 study drug administration or if the stop date/time is before Day 1 study drug administration.
- If the start day and month are missing but the start year is complete, an AE will only be excluded as being treatment emergent if start year is before the year of Day 1 study drug administration or if the stop date/time is before Day 1 study drug administration.
- If the start date is completely missing, an AE will be considered treatment-emergent unless the stop date/time is before Day 1 study drug administration.

These imputations will be used for determining treatment emergence for adverse events; the unimputed partial dates will be included in the data listings.

Adverse events are summarized by subject incidence rates; therefore, in any tabulation, a subject contributes only once to the count for a given SOC or preferred term.

The number and percentage of patients with any treatment-emergent AE (TEAE) and with any related TEAE, with any Grade  $\geq 3$  TEAE, with any serious TEAE, and with any TEAE leading

to withdrawal of study drug, and will be tabulated. In these tabulations, related is defined as any TEAE deemed possibly, probably or definitely related to study drug by the investigator.

Tabulations by SOC and PT will also be produced for all treatment-emergent AEs and for serious TEAEs, presented in alphabetical order by SOC and PT.

No formal hypothesis-testing analysis of adverse events incidence rates will be performed.

All adverse events occurring on study will be listed in subject data listings. By-subject listings also will be provided for the following: subject deaths; serious adverse events; and adverse events leading to treatment withdrawal or death.

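### SAP 4.6.2 defines treatment emergence by onset alone, so an adverse event carried over from MITO-001 that worsens on MITO-002 drug is left out of every TEAE table unless the eCRF opens a new record

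*SAP*

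**What the plan says.** SAP 4.6.2 contains three pieces of text on treatment emergence.

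- **Definition.** A TEAE is "defined as any AE with onset after Day 1 of drug administration". Worsening is not mentioned.
- **Worst-case sentence.** When a start date or time is partly or wholly missing, the event is presumed treatment-emergent unless it can be shown that it "did not occur or worsen during the treatment-emergent period (worst case approach". The SAP does not define that period.
- **Date rules.** With a complete date but no time, "an AE will only be excluded as being treatment emergent if the start date is before the date of Day 1 study drug administration". With month and year only, the test is "if the start month/year is before the month/year of Day 1 study drug administration". With year only, it is "if start year is before the year of Day 1 study drug administration". Each of these also allows exclusion when the event stopped before Day 1 dosing. For a wholly missing date: "If the start date is completely missing, an AE will be considered treatment-emergent unless the stop date/time is before Day 1 study drug administration". None of the four refers to worsening.

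The classification feeds the overall rows (any TEAE, then "with any related TEAE, with any Grade" 3 or higher, serious, and leading to withdrawal of study drug) and the tables by SOC and preferred term for all TEAEs and for serious TEAEs.

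Protocol 11.1 ties treatment emergence to an event being reported after a dose of study drug. It has no worsening clause either. SAP section 5 does not mention the definition.

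**The concern.** MITO-002 subjects enter while already taking RP103, and Day 1 is also the MITO-001 exit visit. Footnote a to the protocol's schedule of events lets ongoing adverse events be carried into the extension database. Protocol 10.1.2 and 10.1.3 ask sites to record changes in events already reported. Some events will therefore have a start date before Day 1 and a clinically relevant course after it. In a long-term safety extension, worsening of such an event is one of the things the AE tables should show.

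An onset-only definition cannot show it. If a carried-over event rises in grade, becomes serious or leads to withdrawal of study drug, but stays on one record with its original start date, it is not a TEAE and drops out of every row at once. SAP section 5 also removes the analysis of seizure activity and the AE summaries by severity and by relationship. The TEAE tables are then the only AE incidence tables that SAP 4.6.2 describes.

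**Working it through.** The plan gives no figure to reproduce. The check applies each part of SAP 4.6.2 to the same kinds of event and compares the results.

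**Inputs.** The definition, worst-case sentence and date rules (SAP 4.6.2); Day 1 as the first day of study drug administration (SAP 4.2.8); the first MITO-002-labelled dose on the evening of Day 1 (protocol 9.5); carry-forward of ongoing events (protocol section 2, footnote a); recording of changes (protocol 10.1.2 and 10.1.3).

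| Event | Definition | Worst-case sentence | Date rules |
|---|---|---|---|
| 1. Complete start date before Day 1, worsens on MITO-002 drug, same record | Not a TEAE | Does not govern a complete date and time; its worsening concept would count it | Excluded on start date if only the time is missing |
| 2. As 1, but start known only to a month or year before that of Day 1 | Not a TEAE | TEAE, because it did worsen | Excluded on start month or year |
| 3. As 1, but start date wholly missing | Cannot be applied | TEAE | TEAE, if not stopped before Day 1 dosing |
| 4. As 1, but worsening opens a new record dated after Day 1 | TEAE | Not needed | Not needed |
| 5. New onset after Day 1 | TEAE | Not needed | Not needed |

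**Reading the table.**

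- Row 1 is the core of the point. The event worsened on study drug and no operative rule counts it.
- Row 2 is a conflict inside the missing-date text: the general sentence keeps the event, while the specific rules exclude it.
- Rows 1 and 3 describe the same clinical course, but the classification turns on whether the start date was completed.
- Row 4 shows the condition. If worsening always opens a new record, the loss does not arise. The schedule footnote leaves data-entry rules to the eCRF instructions, which are not in the documents, and the visit procedures do not say whether a change goes on the old record or a new one.

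**Scale of one misclassified subject.** If a subject has no other event in a row, the row moves by 100 × 1/N percentage points.

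- N = 25 (protocol 12.3): 100/25 = 4.0 points.
- N = 35 (SAP 4.1): 100/35 = 2.86, or about 2.9 points.

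Both are planned maxima. The study closed early (SAP 1.1), so the actual N may be smaller and the step larger. This is the step size for one subject, not an estimate of how many are affected.

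**The case against.** The strongest reply is that nothing is shown to be lost. The omission depends on eCRF conventions the documents do not give, and a new record on worsening would resolve it. That stands, and makes the conclusion conditional.

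Second, the worst-case sentence formally governs only partial or missing start dates. A reader might infer that the SAP states two rival TEAE definitions for every event. It does not: for a complete date and time, only the onset definition applies. What remains is that a missing-date rule uses a wider concept than the definition it serves.

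Third, the date rules say when an event may be excluded. Read strictly, they set a necessary condition and do not order exclusion of every earlier onset. That softens row 2, but does not help row 1, where the definition itself omits the event.

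Fourth, protocol 11.1 also lacks a worsening clause, so on that point the SAP has not departed from the protocol. That is correct, though it means neither document covers the case.

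A reader might also infer that events on the evening of Day 1, after the first MITO-002-labelled dose, are excluded when their time is known. Taken literally, onset after Day 1 would do that. But the same section says "the date/time will be compared as far as possible with the date/time of the start of administration of study drug", and the date rules refer to Day 1 study drug administration. In context the phrase most likely means after the Day 1 dose, so only ambiguous wording remains.

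Finally, the consequences are limited. All on-study events are listed by subject, with separate listings for deaths, serious events and events leading to treatment withdrawal or death. Disposition tabulates reasons for withdrawal. There is no hypothesis test on AE rates, and the report is abbreviated. This stands and sets the severity.

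**Conclusion.** The point holds as a minor defect in the analysis definition. SAP 4.6.2 classifies by onset only, uses a wider concept for missing dates, and gives date rules that ignore worsening. As written, a carried-over event with a complete start date before Day 1 that worsens on MITO-002 drug is counted in no TEAE table.

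This rests on one assumption the documents neither confirm nor rule out: that worsening is recorded on the existing AE record. The number of subjects affected cannot be derived. Confidence is medium because of that condition.

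The documents do not support a claim that safety events are concealed or that a study conclusion changes. The tables are descriptive and the listings retain the events.

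**What to change.** In SAP 4.6.2:

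1. Replace the definition with: *A TEAE is an AE with onset at or after the date/time of the first MITO-002 dose, or an AE ongoing at that dose that later increases in grade, becomes serious or leads to withdrawal of study drug.* This also removes the Day 1 ambiguity.
2. State that the treatment-emergent period starts at that dose.
3. Add to the partial-date rules: *An AE is not excluded on its start date if a worsening is recorded on or after the first MITO-002 dose, or if the date of a recorded worsening is missing and cannot be shown to precede that dose.* Changing only the reference point in these rules would not be enough, because an event with a partial start date in an earlier month or year could still be excluded despite a later worsening.

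In SAP section 5, note that the definition differs from protocol 11.1.

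The cost is a few sentences and minor programming. TEAE counts may be slightly less favourable. If the eCRF already opens a new record on worsening, the change only documents that practice. Where changes in an ongoing event were not recorded, worsening cannot be identified and the event stays visible only in the listings.

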#### **4.6.3.      Laboratory Data**

Clinical laboratory values will be expressed using the International System of Units (SI) units.

The actual value and change from baseline to each on study evaluation will be summarized at all visits using descriptive statistics for each clinical laboratory parameter, including hematology, clinical chemistry and urinalysis.

All laboratory data including hematology, chemistry, urinalysis and serum pregnancy will be provided in data listings.

#### **4.6.4.      Vital Signs and Physical Examinations**

The actual value and change from baseline to each on study evaluation will be summarized for vital signs. By-subject listings of vital sign measurements will be presented in data listings.

All abnormal physical examination findings will be presented in a data listing.

#### **4.6.5.      Neurological Examination**

Individual subject changes will be summarized by shift tables. These tables will show the number of subjects who had values that shifted from normal, abnormal – not clinically significant, or abnormal – clinically significant at baseline to normal, abnormal – not clinically significant, or abnormal – clinically significant at the last observed value.

Abnormal neurological examination findings will be provided in a data listing.

#### **4.6.6.      Electrocardiogram**

Individual subject changes will be summarized by shift tables. These tables will show the number of subjects who had values that shifted from normal, abnormal – not clinically significant, or abnormal – clinically significant at baseline to normal, abnormal – not clinically significant, or abnormal – clinically significant at each visit and the last observed value.

All ECG data for each subject will be provided in data listings.

#### **4.6.7.      Concomitant Medications**

Concomitant medications will be coded using the WHO Drug dictionary. The use of concomitant medications will be included in by-subject data listing.

## **5. CHANGES TO PLANNED ANALYSES**

The study was closed prematurely and results will be summarized in an abbreviated clinical study report. Thus, certain analyses described in the protocol (all efficacy analyses, pharmacokinetic and pharmacodynamic analyses, analysis of seizure activity, summaries of AEs by severity, AEs by relationship to study drug, and AE method of collection) will not be performed.

6.

1

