Statistical Analyses:	
This extension study is designed to assess the efficacy, safety and tolerability of RP103 delayed-release cysteamine bitartrate capsules in patients with inherited mitochondrial disease.
 
The sample size will be up to 25 subjects (the maximum number of participants planned for Study RP103-MITO-001)
 
Any interim analyses will be described in detail in the statistical analysis plan (SAP), which will be developed and specify the statistical methods to be used. The SAP will be finalized prior to

	
data cutoff or database lock for the subsequent analysis. Demographic and disposition data, drug administration, medical history, prior and concomitant medications, adverse events, clinical laboratory measurements, vital signs, ECG measurements, physical examination findings, and all other safety data will be listed by subject and timepoint. Descriptive statistics will be tabulated for change and shift from Baseline in the safety laboratory variables (chemistry, hematology, urinalysis), vital signs and ECGs. Adverse events will be summarized by method of collection type, frequency, severity, relationship to study drug, any change in study drug administration, and number of subjects per treatment.
 
Adverse events will be categorized using MedDRA, and listed by verbatim, primary term and system organ class (SOC).

--	---

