### **7.3. Study Drug Dosing Methodology**

Upon RP103-MITO-002 study entry, subjects will continue on the last total daily dose of RP103 taken during the previous RP103-MITO-001 study. Subsequent RP103 dose adjustments are permitted (e.g. as the subject grows, or if deemed necessary by the Investigator for tolerability reasons).

The Sponsor's medical officer may be consulted for assistance making RP103 dose adjustment decisions at any time during the study. NOTE: For each subject, when calculating the number of capsules to be taken every 12 hours (i.e. half of the prescribed total daily dose), if rounding is required to get a whole number of capsules to be taken, then rounding should be down and not up.

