## 12. STATISTICAL PLAN

### 12.1. Statistical Methods

This open-label extension study is designed to assess the safety, tolerability and efficacy of Cysteamine Bitartrate Delayed-release Capsules (RP103) for treatment of children with inherited mitochondrial disease.

The sample size will be up to 25 subjects (the maximum number of participants planned for study RP103-MITO-001).

Any interim analyses will be described in detail in the statistical analysis plan (SAP), which will be developed and specify the statistical methods to be used. The SAP will be finalized prior to data cutoff or database lock for the subsequent analysis. Demographic and disposition data, drug administration, medical history, prior and concomitant medications, AEs, clinical laboratory measurements, vital signs, ECG measurements, physical examination findings, and all other safety data will be listed by subject and timepoint. Descriptive statistics will be tabulated for change and shift from Baseline in the safety laboratory variables (serum chemistry, hematology, and urinalysis), vital signs, [score names] scores and ECGs. Adverse events will be summarized by method of collection type, frequency, severity, relationship to study drug, any change in study drug administration, and number of subjects per treatment. Safety laboratory values outside reference ranges will be flagged in laboratory listings.

AEs will be categorized using MedDRA, and listed by verbatim, primary term and SOC. SAEs will include MedDRA coding of primary and secondary (non-serious) event terms.

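### The SAP narrows the protocol's summary of adverse events by change in study-drug dosing to withdrawals only, and its list of changes does not say so

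*SAP*

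**What the plan says.** Protocol 12.1 states: "Adverse events will be summarized by method of collection type, frequency, severity, relationship to study drug, any change in study drug administration". The synopsis repeats the commitment: "relationship to study drug, any change in study drug administration, and number of subjects per treatment". The item is therefore not a stray phrase.

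The SAP was written after the sponsor closed the study early, and it describes safety analyses only (SAP 1.1). Its overall TEAE table in 4.6.2 counts subjects with any TEAE, any related TEAE and any TEAE of Grade 3 or above, and then, across a page break, those "with any serious TEAE, and with any TEAE leading" "to withdrawal of study drug, and will be tabulated". On breakdowns by system organ class and preferred term, it says: "Tabulations by SOC and PT will also be produced for all treatment-emergent AEs and for serious TEAEs". The dedicated AE listings cover deaths, serious events and "adverse events leading to treatment withdrawal or death".

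SAP Section 5 names the protocol analyses that fall away: efficacy, pharmacokinetics, pharmacodynamics, seizure activity, and finally "summaries of AEs by severity, AEs by relationship to study drug, and AE method of collection) will not be performed".

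On dosing, Protocol 7.3 allows the dose to be adjusted after entry, for example with growth or "if deemed necessary by the Investigator for tolerability reasons". SAP 2.1 repeats this, and SAP 1.2 keeps tolerability in the primary objective.

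**The concern.** With dose adjustment for tolerability permitted, intolerance can show up as a changed dose in a subject who stays on treatment. That is the information the protocol's summary by change in drug administration would have carried. If only withdrawals are counted, a subject kept on drug through AE-driven dose cuts looks the same in the action-related row of the TEAE table as a subject who never needed a change.

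This matters more than usual because safety and tolerability are all that remain to be reported. Entry is also limited to subjects who completed every visit of RP103-MITO-001. It is a reasonable inference from the design, though not a documented fact, that withdrawals for AEs may be few in such a group and so a blunt measure of tolerability.

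There is a reporting side too. Someone reading Section 5 to learn how the analysis departs from the protocol would conclude that the summary by dosing change is still being produced in full.

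**Working it through.** No formula applies and the plan gives no figure to reproduce. The check is an item-by-item comparison.

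**Step 1. Protocol items against the SAP.** The sentence in Protocol 12.1 has five AE dimensions, plus the number of subjects.

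| Protocol item | What SAP 4.6.2 keeps | Declared in SAP Section 5? |
|---|---|---|
| Method of collection | Nothing | Yes |
| Frequency | Subject incidence, overall and by class and term | Not needed |
| Severity | One row: Grade 3 or above | Yes |
| Relationship to drug | One row: any related TEAE | Yes |
| Change in drug administration | One row: TEAEs ending treatment, plus a listing | **No** |
| Number of subjects | Subject incidence | Not needed |

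**Step 2. The SAP's own standard for declaring a change.** Severity and relationship each survive as a single row, and Section 5 still declares both summaries as not performed. Change in drug administration is cut back in the same way, to a single row, but is not declared. By the SAP's own practice it belonged on the list.

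**Step 3. Can another described summary fill the gap?** SAP 4.6.1 gives duration of exposure and the number of days with a missed dose. Neither is linked to AEs, and there is no summary of dose level. A lowered dose taken as prescribed adds no missed-dose days. An interruption might raise the missed-dose count, but it would not be attributed to an AE.

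**Step 4. Can listings fill the gap?** In part. SAP 4.2.7 promises that everything on the case report form will be listed, 4.6.1 promises a record per dosing event, and 4.6.2 promises a listing of every AE. A reader could try to match dose records with AE dates subject by subject. The SAP does not say that the AE listing will show what was done with study drug in response to each event.

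**Step 5. What cannot be checked.** The SAP's contents page shows a Section 6 listing tables and listings, but its content is not in the text available. A table of AEs by action taken could be named there, although 4.6.2 describes none.

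**The case against.** The strongest reply is that little is lost. Development has ended, an abbreviated report is planned, and the analysis is single-arm and descriptive with no hypothesis test. Tolerability does not rest on the withdrawal row alone, since all TEAEs by class and term, related TEAEs, Grade 3 or above and serious TEAEs remain. With at most 25 subjects (protocol) or 35 (SAP 4.1), by-subject listings are short enough to read. Section 5's silence also has an innocent reading: the analysis was not dropped and appears in Section 6.

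Most of this stands as a limit on the point. It sets the importance at moderate and makes the conclusion conditional on Section 6. It does not remove the mismatch. Early closure explains cutting analyses, but not leaving one off an itemised list, and a reader working through listings does not have the count that the protocol planned.

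Four stronger readings might be inferred, and the documents do not support them:

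- That the summary has been removed altogether. It has been narrowed: withdrawal is itself a change in drug administration, and it is both tabulated and listed.
- That AE-driven dose changes will be absent from the report. The listings may contain them.
- That the protocol provides for temporary interruption as a response to intolerance, or for dose changes at any time. Section 7.3 speaks of dose adjustments and does not mention interruption. Its wording about any time concerns consulting the sponsor's medical officer.
- That the report will present a low withdrawal rate as proof of tolerability. Neither document says this.

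**Conclusion.** The point holds on the visible text. The protocol's AE summary by change in study-drug administration is reduced to withdrawals, and SAP Section 5 does not declare the reduction, although it declares the parallel reductions for severity and relationship. As written, no described summary counts subjects whose AEs led to a dose change short of withdrawal.

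No numerical size can be given. The documents do not report how many dose changes occurred or why, so any percentage would only reflect the inputs chosen for it. No test, estimate or sample size depends on this. What is affected is what the report can say about tolerability and the accuracy of its account of departures from the protocol. It should be corrected, but it does not undermine the safety analysis.

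The conclusion rests on two assumptions: that Section 6 does not already specify such a table, and that the response to each AE was recorded with respect to study drug. The protocol's planned summary implies the second, but the case report form is not available to confirm it.

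**What to change.** First check SAP Section 6. If it already contains a table of AEs by action taken with study drug, describe that table in 4.6.2 and nothing more is needed.

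If it does not, add to the overall TEAE table in 4.6.2 the number and percentage of subjects with any TEAE leading to (a) dose reduction, (b) interruption, if recorded, (c) withdrawal, and (d) any of these. Use the data that the protocol planned to summarise. State in the same section that the all-AE listing will show the action taken with study drug, which avoids a separate listing.

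If the sponsor prefers not to add the rows, add a clause to Section 5 stating that the summary by change in drug administration is limited to withdrawals, and do not rest tolerability statements in the report on withdrawals alone.

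The cost is a few rows in an existing table, or one clause. The tolerability figure may look somewhat less favourable. Neither route alters any dosing rule.
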